6.4.3 Other Efficacy-related Summaries

The following are additional efficacy analyses to be performed.

Select summaries and tabulations of efficacy endpoints, including subgroup analyses, will be also presented using boxplots with raw data points indicated on the plots.

6.4.3.1 Change in SBP from End of Treatment to End of Study

Analysis of change in office-measured SBP from End of Treatment (Study Week 8 or last measurement prior to starting the rescue medication) to End of Study (Study Week 12 for Part 1 and Study Week 10 for Part 2) will be analyzed using an ANCOVA model with treatment group as a factor and SBP at EOT as a covariate.

A least-square estimate, along with the 90% CI, of the mean difference between each dose group and the placebo group will be provided for each time point. P-values corresponding to the pairwise tests, not adjusted for multiplicity, of the difference between each dose group vs placebo will also be provided.

6.4.3.2 Comparison between 100mg QD and 25mg BID in Change from Baseline to Week 8 in SBP

Subjects randomized to 100mg QD in Part 1 and 2 and 25 BID dose in Part 1 will be included in this analysis.

The two dose levels, 100mg QD and 25mg BID will be tested for the equality of distributions using Kolmogorov-Smirnov test. If the distributions of responses are considered comparable across dose

and PRA levels at baseline, the dose groups will be pooled. This dataset will be used to repeat efficacy analyses, including the primary and select subset analyses.

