##### **3.2.3. Safety Endpoints**

- Incidence and severity of all spontaneously reported adverse events (AEs)
- Changes in vital signs (SBP, DBP, body temperature, heart rate, and respiratory rate)
- Changes in electrocardiogram parameters (including cardiac intervals: PR, QRS, QT, and corrected QT interval using Fridericia's formula)

- Changes in clinical laboratory assessments (hematology, chemistry, coagulation, and urinalysis)
- Change in office-measured SBP from Study Week 8 (end-of-treatment period) to Study Week 12 for Part 1 and Study Week 10 for Part 2 (end of follow-up)

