### **9.4. Handling of Missing Data**

Given the preliminary nature of this study, no formal imputation for missing data is planned. For the office-measured efficacy endpoints, values post rescue medications will be set to missing and imputed using the last value observed before start of rescue medication. All other missing values will not be imputed.

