3.4 Safety Endpoints

The protocol describes as safety endpoints the following:

- Incidence and severity of all spontaneously reported adverse events (AEs)
- Changes in vital signs (standing SBP, standing DBP, body temperature, heart rate, and respiratory rate)
- Changes in electrocardiogram parameters (including cardiac intervals: PR, QRS, QT, and corrected QT interval using Fridericia's formula)
- Changes in clinical laboratory assessments (hematology, chemistry, coagulation, and urinalysis)
- Change in office-measured SBP from Study Week 8 (end-of-treatment period to end of follow up (i.e. end of Study Week 12 for Part 1 and end of Study 10 for Part 2).

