6.7.6 Concomitant Medications

Prior medications are defined as any medications taken and stopped prior to the start of the study drug (including during the placebo run-in period).

Concomitant medications are defined as any medication or vaccine (including over-the-counter or prescription medicines, recreational drugs, vitamins, and/or herbal supplements) with a start date on or after the first study drug administration (following randomization) or medications with a start date prior to first study drug administration but ongoing or with stop dates on or after first study drug administration. Medications that stop during the placebo run-in period will be considered prior medications. Medications with a start date after last study drug administration will not be considered as concomitant medications; these post-treatment medications will be identified in the listing.

The number and percentage of subjects with concomitant medications will be summarized by WHO-DD Anatomical-Therapeutic-Chemical 4 (ATC4) classification and PT by treatment group and the combined active treatment groups pooled together. The summary table will display counts and percentages of subjects who reported using at least 1 concomitant medications in any of the treatment groups. Subjects may have more than 1 medication per ATC4 classification. At each level of subject summarization, a subject will only be counted once if he/she reports 1 or more medications.

A similar summary table will be created for rescue medication data. Rescue medications are defined as any anti-hypertensive treatment that starts between the first administration of the double-blind study drug and either the last administration of the double-blind study drug or the AOBP assessment at week 8, whichever occurs later. Time from baseline to initiation of rescue medication will be analyzed by treatment group using Kaplan-Meier methods. Subjects without rescue medication by Week 8/EOT will be censored at this date. A cumulative incidence plot of the proportion of subjects initiating rescue medication at each Study Visit will also be presented by treatment group.

Only concomitant and rescue medication data will be summarized but a listing of all prior, concomitant, and post-treatment medication data will be provided. This listing will also include an indicator column specifying whether the medication is an AHT or thiazide diuretic.

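### SAP 6.4.3.1 starts rescued subjects' off-treatment SBP change before rescue instead of at Week 8, without declaring it, and has no rule for End of Study readings taken on an added antihypertensive

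*SAP*

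**What the plan says.** Protocol 3.2.3 lists the endpoint under safety: "Change in office-measured SBP from Study Week 8 (end-of-treatment period) to Study Week 12 for Part 1 and Study Week 10 for Part 2". SAP 3.4 repeats it in the same form: "Change in office-measured SBP from Study Week 8 (end-of-treatment period to end of follow up". Neither has a special start value for rescued subjects.

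SAP 6.4.3.1, placed among the efficacy summaries, takes the change from "End of Treatment (Study Week 8 or last measurement prior to starting the rescue medication) to End of Study". It fits an "ANCOVA model with treatment group as a factor and SBP at EOT as a covariate" and gives LS differences from placebo with 90% CIs and p-values. The end value carries no condition on antihypertensive use.

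Four other rules bear on it:

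- SAP 6.7.6 defines rescue as an antihypertensive begun between the first double-blind dose and the later of the last dose and the Week 8 AOBP.
- The same section says: "Medications with a start date after last study drug administration will not be considered as concomitant medications". These drugs are identified in a listing that carries an antihypertensive indicator.
- Protocol 9.4, for office-measured efficacy endpoints, says: "values post rescue medications will be set to missing and imputed using the last value observed before start of rescue medication". SAP 6.2.6 imputes nothing unless a section says otherwise.
- Protocol 4.1 keeps a subject who is given an antihypertensive in the study and lets the investigator adjust background therapy.

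SAP section 7 lists two departures from the protocol: no pooling of Parts 1 and 2, and the timing of ABPM. The start value of this endpoint is not among them.

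**The concern.** The endpoint should show what happens to SBP when study drug stops. For a rescued subject, SAP 6.4.3.1 moves the start back to before rescue but leaves the end at the last visit, where the rescue drug may still be in use. If rescue began at Week 3 and study drug continued, the interval also takes in the remaining treatment weeks to Week 8. The resulting change is not an off-treatment change.

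The second gap is separate. If SBP rises after the last dose and an antihypertensive is started in follow-up, the treated End of Study reading enters the analysis unmarked. The start value for such a subject is correctly Week 8; only the end value is affected. Yet this is the subject in whom the endpoint ought to detect a rise.

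SAP 6.4.3.1 is the only between-arm model in the SAP for SBP change after stopping, so a reader looking for rebound will rely on it.

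**Working it through.** **1. The definitions side by side**

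| Source | Start, rescued subject | Start, others | End |
|---|---|---|---|
| Protocol 3.2.3, SAP 3.4 | Week 8 | Week 8 | Week 12 / Week 10 |
| SAP 6.4.3.1 | last reading before rescue | Week 8 | Week 12 / Week 10 |

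**2. One rescued subject.** Let W be the rise on stopping study drug and R the fall due to the added drug.

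- Pre-rescue start, observed end on rescue: change = W − R. With W = R = 10 mmHg (assumed), the change is 0 and the rise is hidden.
- Pre-rescue start, protocol 9.4 carry-forward: the end equals the start, so the change is 0 whatever W is.
- Week 8 start, rescue unchanged at both readings: change = (W − R) − (−R) = W.

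**3. The plan's own precision, for scale.** The protocol synopsis gives ±3.8 mmHg for the Week 8 contrast with 30 per arm, SD 9 and a two-sided 90% CI. Check: 1.645 × 9 × √(2/30) = 3.82. No figure is given for the off-treatment endpoint.

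**4. Unadjusted arm means.** With a share p affected, each arm mean shifts by −R·p and the active-minus-placebo difference by R·(p_placebo − p_active). The documents supply neither p nor R. Assumed ranges: p from 5% to 30%, R from 5 to 15 mmHg.

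| p active / placebo | R = 5 | R = 10 | R = 15 |
|---|---|---|---|
| 5% / 5% | 0 | 0 | 0 |
| 5% / 20% | +0.75 | +1.5 | +2.25 |
| 5% / 30% | +1.25 | +2.5 | +3.75 |
| 20% / 5% | −0.75 | −1.5 | −2.25 |

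**5. The planned model.** The SAP adjusts for SBP at EOT, so step 4 is not the answer for the planned contrast. A large-sample simulation of the ANCOVA used these assumptions: between-subject SD 10, visit SD 6.4, W = 10, R = 10. Without a rescue effect the contrast is 7.1, not 10, because the covariate itself differs between arms: 10 × 100/(100 + 6.4²) = 7.1. The comparison is therefore with 7.1.

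| p active / placebo | Rescue to the highest EOT SBP | Rescue unrelated to EOT SBP |
|---|---|---|
| 5% / 5% | 6.2 | 7.1 |
| 5% / 15% | 6.7 | 8.1 |
| 5% / 20% | 7.0 | 8.6 |
| 5% / 30% | 7.7 | 9.6 |
| 20% / 5% | 4.0 | 5.6 |

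When rescue follows high readings, equal rates do not protect the contrast (6.2 against 7.1). At 5% / 15%, step 4 gives 10 × (0.15 − 0.05) = +1.0, while the ANCOVA gives 6.7 − 7.1 = −0.4. The sign reverses.

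**6. Would excluding affected subjects repair it?** Take SD 9 for the change (the synopsis figure for change from baseline, borrowed here) and the extreme case in which the subjects starting a drug are those with the largest rise. Dropping the top share p lowers the mean by 9·φ(z)/(1 − p), where z is the upper-p normal quantile.

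| p | Rise hidden by exclusion | Rise hidden if left in, R = 10 |
|---|---|---|
| 10% | 1.75 | 1 |
| 20% | 3.15 | 2 |
| 30% | 4.5 | 3 |

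In this extreme case, exclusion hides more than it recovers.

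**The case against.** The pre-rescue start is not arbitrary: it is the value the primary estimand uses for a rescued subject at Week 8, so each subject has a single EOT value. That is a reason for the choice. It does not make the interval an off-treatment one, and it does not explain why two endpoint lists say Week 8 and section 7 is silent.

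The 9.4 carry-forward is limited to efficacy endpoints, this endpoint is listed as safety, and the SAP default is no imputation. So a forced change of 0 is probably not intended. That stands, but the analysis sits in the efficacy section, and one sentence would settle it.

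Drugs started after the last dose are not lost, since the listing flags antihypertensives. That also stands. What is missing is a count by arm and any link to the End of Study reading.

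The stakes are modest: this is an additional summary in a mainly descriptive study without multiplicity control, and most of the simulated shifts are smaller than ±3.8 mmHg.

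A reader might infer that the endpoint measures the added drug rather than the stopping of MLS-101. The documents do not support that. Subjects with no added antihypertensive have a plain Week 8 to End of Study change, and in affected subjects the two effects are summed. Nor do the documents say that rescue is more common on placebo, that it is still in use at the last visit, or that new drugs are common in follow-up.

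**Conclusion.** The concern holds in limited form. SAP 6.4.3.1 departs from the endpoint as defined in protocol 3.2.3 and SAP 3.4, the departure is undeclared, and in rescued subjects it mixes the effect of stopping with an added drug and possibly with on-treatment weeks. An antihypertensive begun after both the last dose and the Week 8 AOBP falls outside every analysis rule.

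The size in this trial cannot be stated. Under the assumptions in steps 4 and 5, the unadjusted difference moves by −2.25 to +3.75 mmHg. With rescue going to the highest readings, the ANCOVA contrast moves by −3.1 to +0.6 mmHg (4.0 and 7.7 against 7.1). The direction depends on the rates in each arm and on how closely rescue follows SBP, so a bias of known sign should not be claimed. The inconsistent start value needs no assumption and should be corrected.

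**What to change.** In SAP 6.4.3.1:

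1. Use the observed Week 8 SBP as both the start value and the ANCOVA covariate for all subjects, as protocol 3.2.3 and SAP 3.4 define it.
2. State that the protocol 9.4 carry-forward does not apply to this endpoint.
3. Keep the all-observed analysis as the main one.
4. Tabulate by arm the subjects who start or increase an antihypertensive between Week 8 and End of Study. A difference between arms is itself informative about rebound.
5. Add, as supplementary only, the analysis limited to subjects with no such start or increase, with a note that it selects on a post-randomisation event that may be driven by the outcome (step 6). A subject on unchanged rescue at both readings stays in.

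The cost is SAP wording and a little programming, since post-treatment medications and the antihypertensive indicator are already planned for the listing. Two small downsides: rescued subjects no longer share the primary estimand's pre-rescue value, and a rescued subject without a Week 8 reading drops out of this analysis. The fix does not remove the effect of drugs added in follow-up from the main estimate; it makes their number visible.

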**Statistical Methods:**

[figure not shown]
The primary estimand in the study aims to answer the research question on the treatment effect of investigational therapy versus placebo in addition to standard of care on the change in office-measured blood pressure from baseline to Week 8. Data summaries for this study will be primarily descriptive in nature. Both safety and efficacy will focus on subjects receiving at least 1 dose of study treatment. Endpoints measured as categorical outcomes (including binary endpoints) will be summarized as frequencies and percentages. Continuous endpoints will be summarized using the following descriptive statistics: sample size, mean, median, quartiles and standard deviation. For efficacy endpoints, confidence intervals and tests of significance will use a 10% (2-sided) significance level. Given the exploratory nature of this study, no adjustments for multiplicity will be used.

*Sample Size*

This study has been designed to provide preliminary information regarding the appropriate dose and frequency of dosing for MLS-101 with respect to changes in SBP after 8 weeks of treatment. The sample size has been determined to provide estimates of the placebo-adjusted mean change in SBP from baseline for each dose that are of adequate precision assuming a 90% 2-sided confidence interval and an effect size of 10.0. With 30 subjects planned per arm in Part 1, the mean placebo adjusted change from baseline in SBP for each dose will be estimated with a precision of  $\pm 3.8$ , assuming a standard deviation of 9 in the subject level changes in SBP from baseline. All analyses based on Part 2 of the study will be exploratory in nature; no formal sample size considerations will be made for Part 2.

The study schema for Study MLS-101-201 is presented in [Figure 1](#). The SoA are presented in [Table 1](#) and Table 2 for Part 1 and Part 2 of the study, respectively. Detailed descriptions of study assessments are provided in [Section 4.8](#) and [Section 8](#).

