2 STUDY DESIGN

2.1 Introduction

This is a Phase 2 randomized, double-blind, placebo-controlled, dose-ranging, multicenter study designed to evaluate the effect of orally administered MLS-101 on BP for the treatment of uncontrolled hypertension (hypertensive despite receiving ≥ 2 antihypertensives) when used as add-on therapy to stable background treatment in male and female subjects ≥ 18 years of age.

The study consists of two parts. For enrollment into Part 1 of the study, a subject's value of PRA must be ≤ 1 ng/mL/h based on morning measurement. If the value of PRA > 1 ng/mL/h based on morning measurement, then subjects may be eligible to enter Part 2 of the study.

The initial estimate is that approximately 1100 subjects will undergo up to 2 weeks of pre-Screening for Part 1 and 4 weeks of pre-Screening for Part 2. It is estimated that approximately 270 subjects will have qualifying plasma renin activity (PRA) and serum aldosterone levels to be eligible to enter Screening/start of Placebo Run-in for Part 1 after completing a Screening/main study informed consent form (ICF) that has been approved by the Institutional Review Board (IRB). Assuming a 40% screen-failure rate during Run-in, a total of 160 subjects will meet all eligibility requirements to qualify for enrollment in the study.

For Part 2, it is estimated that approximately 60 subjects will have qualifying PRA and serum aldosterone levels to be eligible to enter Screening/start of Placebo Run-in for Part 2 after completing a Screening/main study ICF that has been approved by the IRB. Assuming an approximately 40% screen failure rate, a total of 36 subjects will meet all eligibility requirements to qualify for enrollment in Part 2 of the study.

In the previous version of the protocol, subjects in Part 1 of the study were randomized into 6 equal treatment groups (1:1:1:1:1:1) to 12.5 mg BID, 25 mg BID, 12.5 mg QD, 50 mg QD, 100 mg QD, or placebo. After a review of the clinical data at the December 2021 interim analysis, it was decided that the 2 lowest dose levels (12.5 mg QD and 12.5 mg BID) will be dropped due to a lack of consistent meaningful reduction of blood pressure. Effective with Amendment 4, subjects will be randomized into 4 equal treatment groups (1:1:1:1) to 25 mg BID, 50 mg QD, 100 mg QD, or placebo. All 6 treatment groups will be presented in this analysis plan.

[figure not shown]

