6.2.2 Definition of Baseline

Baseline is defined as the last available observed value of the parameter of interest prior to the first administration of the investigational medicinal product (IMP) for the double-blinded treatment period.

For AOBP measurements and any other clinical or laboratory variable for which there are replicate evaluations at the screening and baseline visits, baseline is defined as the mean of the last two non-missing values prior to first administration of the IMP for the double-blinded treatment period.

Change from baseline is calculated as: post-baseline result – baseline result.

Percentage change from baseline is calculated as: (change from baseline / baseline result) x 100%.

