6.2.3 Adjustments for Covariates

Efficacy models with continuous variables based on SBP as the response variable (e.g. change from baseline in office-measured SBP, mean daytime SBP) will have the corresponding baseline value as a continuous covariate.

Similarly, models based on DBP will include the corresponding baseline DBP value as a continuous covariate.

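### The off-treatment SBP analysis adjusts for end-of-treatment SBP, which an effective dose has already lowered, so it understates any rise after stopping

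*SAP*

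**What the plan says.** SAP Section 6.4.3.1 takes the change in office SBP from EOT to EOS (Week 12 in Part 1, Week 10 in Part 2) and states that it "will be analyzed using an ANCOVA model with treatment group as a factor and SBP at EOT as a covariate". The starting point is "End of Treatment (Study Week 8 or last measurement prior to starting the rescue medication", so the covariate is always a value taken after randomization. The output is "A least-square estimate, along with the 90% CI, of the mean difference between each dose group and the placebo group", with unadjusted pairwise p-values.

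The endpoint comes from Protocol Section 3.2.3, which lists among the safety endpoints "Change in office-measured SBP from Study Week 8 (end-of-treatment period) to Study Week 12 for Part 1 and Study Week 10 for Part 2". SAP Section 3.4 repeats it.

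Elsewhere the SAP treats covariates differently. Section 6.2.3 says that continuous efficacy models with SBP as the response "will have the corresponding baseline value as a continuous covariate", and Section 6.2.2 states that "Baseline is defined as the last available observed value of the parameter of interest prior to the first administration" of double-blind study drug.

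**The concern.** Adjusting a change for its starting value is ordinary ANCOVA when that value precedes randomization, because the arms then share the same expected starting level. Here the starting value is the primary efficacy variable at the primary time point, or the last value before rescue. If a dose works, its arm starts the off-treatment period lower than placebo. The model then compares treated and placebo subjects who happen to have the same on-treatment SBP. Randomization does not protect that comparison, and it is not the difference in post-treatment change.

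The stake is the reading of what happens after stopping. Section 6.4.3.1 supplies the only planned between-arm estimate, confidence interval and p-value for this endpoint. The vital-sign summaries in SAP Section 6.7.3 cover temperature, pulse and respiratory rate, not seated SBP. For effective doses the estimate is shifted towards understating a rise, and it can show a further fall where there is none.

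**Working it through.** **Inputs**

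- Placebo-adjusted effect at EOT, D = 10, the protocol synopsis planning effect size of 10.0, read as mmHg.
- SD of change 9. The synopsis gives it as "assuming a standard deviation of 9 in the subject level changes in SBP from baseline"; it is carried over here to the EOT-to-EOS change, which is an assumption.
- 30 subjects per arm (Part 1) and a 10% two-sided test (synopsis).
- b, the within-arm slope of EOS SBP on EOT SBP: not in the documents, assumed 0.5 to 0.8.

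**Reproducing the plan's precision figure.** 1.645 × 9 × √(2/30) = 3.82, which matches the stated ±3.8. The inputs are therefore read as the sponsor meant them.

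**The shift.** Let C = EOS − EOT. Within an arm, the slope of C on EOT is b − 1. The adjusted treatment coefficient is

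(difference in mean C) − (b − 1) × (difference in mean EOT).

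The difference in mean EOT, dose minus placebo, is −D, so

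**reported = true − (1 − b) × D.**

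- D = 10: (1 − 0.5) × 10 = 5.0; (1 − 0.8) × 10 = 2.0.
- D = 5: 2.5 and 1.0. D = 15: 7.5 and 3.0.
- D = 10 with b outside the range: 7.0 at b = 0.3 and 0.5 at b = 0.95.
- D = 0: no shift.

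**Is the range for b reasonable?** If EOT and EOS variances are equal, SD of change² = 2 × SD² × (1 − b), so b = 1 − 81/(2 × SD²), where SD is that of the SBP level. A level SD of 9.0 gives b = 0.5, 12.0 gives 0.72 and 14.2 gives 0.8. A b of 0.95 would need a level SD of about 28. This is only a plausibility check.

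**Simulation** (two arms, 30 each, SD of change 9, equal EOT and EOS variances, D = 10, 20,000 replicates). Entries are mean estimates in mmHg.

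| True difference in change | Planned model, b = 0.5 | Planned model, b = 0.72 | Planned model, b = 0.8 | Baseline SBP as covariate |
|---|---|---|---|---|
| +15 (5 above placebo) | 10.0 | 12.2 | 13.0 | 15.0 |
| +10 (full return) | 5.0 | 7.2 | 8.0 | 10.0 |
| +5 (half return) | 0.0 | 2.2 | 3.0 | 5.0 |
| 0 (equal change) | −5.0 | −2.9 | −2.0 | 0.0 |

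Rejection rates, in the same order:

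- True 0: 68–69% (two runs), 33%, 22%; with baseline SBP 10%.
- True +5: 10%, 24%, 35%; with baseline SBP 68%.
- True +15: at least 99% with the planned model.

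A separate simulation with different assumptions (level SD 12, baseline–EOT correlation 0.6, 4,000 trials) gave, for a true +10, means of 5.06 (b = 0.5) and 8.00 (b = 0.8) with the EOT covariate, against 10.07 and 10.02 with baseline SBP.

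**Six-arm Part 1 layout** (placebo and three doses with D = 10 at 30 each, two doses with D = 0 at 20 each, true difference 0, 6,000 replicates). For b = 0.5, 0.72 and 0.8 the effective doses are reported at −5.0, −2.8 and −2.0, with rejection in 75%, 35% and 23%. The no-effect doses stay at 0.0 with about 10%. That may describe the two lowest doses, which SAP Section 2.1 says "will be dropped due to a lack of consistent meaningful reduction of blood pressure".

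**Part 2.** The shift does not depend on arm size, and simulation with 30 versus 6 subjects shows the same shift.

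**The case against.** The strongest reply is that Section 6.4.3.1 answers a legitimate conditional question, namely change among subjects with equal EOT SBP, and that it is biased only if the marginal difference in change is the target. The protocol lists the change without specifying a between-arm contrast, and Protocol Section 9.3.2 leaves post-Week 8 analyses to the SAP. But the listed quantity is the change itself, and a contrast between arms on that quantity is the marginal one. The conditional contrast is not protected by randomization, and nothing in the SAP says it is intended.

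Other points stand in part:

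- Section 6.2.3 is written for efficacy models, and a specific rule may override it. The inconsistency is therefore supporting evidence only; the algebra does not need it.
- The size depends on b and D, and the rejection rates also depend on the carried-over SD and on equal variances.
- A 5 mmHg overshoot above placebo is still detected. What is mainly distorted is the size of an ordinary return towards placebo. The corrected contrast shows +10 for a full return without overshoot, so it must be read against the Week 8 effect.
- The simulations contain no rescue use.
- The model sits under other efficacy-related summaries, in an exploratory study without multiplicity control.

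**Conclusion.** The concern holds. As written, the estimate for any dose that lowers SBP at EOT is shifted downwards by (1 − b) × D. Given D = 10 and b from 0.5 to 0.8, that is 2 to 5 mmHg, of the same order as the planned ±3.8 half-width. The direction is certain whenever b is below 1 and the dose has an effect at EOT; the size is conditional on those two values. The likely error is a missed or understated rise, or a false further fall, rather than a false rebound. The primary Week 8 analysis is untouched. The point should be fixed because this is the only comparative analysis of a listed safety endpoint.

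**What to change.** In SAP Section 6.4.3.1, replace SBP at EOT as the covariate with baseline SBP as defined in Section 6.2.2, or report the unadjusted difference in mean change. If the EOT-adjusted model is kept, label it as a supplement that compares subjects with equal on-treatment SBP. Rescued subjects (Section 6.7.6) should stay in the main contrast, as the section now implies; a separate display of them would be descriptive only.

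The cost is one phrase and a rerun of one model. In the two-arm simulation the standard error is essentially unchanged: 2.33 with baseline SBP and 2.31 unadjusted, against 2.32 to 2.35 with EOT SBP. In the six-arm model it is slightly larger for effective doses, 2.32 to 2.33 against 2.13 to 2.26. SAP Section 2.4 records that some sponsor staff were unblinded to support decisions after the interim analyses, particularly at the end of Part 1. A change to the Part 1 model should therefore be dated and documented, as SAP Section 1.1 requires for deviations from the plan.
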